### 1.1.3 Safety objective

Safety Objectives	Outcome Measures
To evaluate the pharmacokinetics and immunogenicity of benralizumab	
 
• Serum PK
 
• Anti-drug antibodies
 

To assess the safety and tolerability of benralizumab	
 
• Adverse events (AEs) and serious adverse events (SAEs)
 
• Laboratory variables
 
• Physical Examination
 

### 1.1.4 Exploratory objectives

Exploratory Objective	Outcome Measures
To evaluate patient impression of overall asthma severity (PGI-S) and overall change from baseline as reported by the patient (PGI-C) and clinician (CGI-C)	
 
• Change from baseline (Visit 4) in PGI-S at all post-baseline assessment timepoints
 
• Clinician-reported global change in asthma from baseline (Visit 4) as measured by CGI-C
 
• Patient-reported global change in asthma from baseline (Visit 4) as measured by PGI-C
 

### 1.1.5 Body plethysmography sub-study objectives

Sub-study Primary Objective	Outcome Measure
To determine the effect of benralizumab on the time course of change in lung function as assessed through body plethysmography	Change from baseline (Visit 4) to end of treatment (Visit 10) in the following measures compared to placebo: 
 
• Residual volume (RV)
 

Sub-study Secondary Objectives	Outcome Measures

To determine the effect of benralizumab on the time course of change in lung function as assessed through body plethysmography	Change from baseline (Visit 4) to end of treatment (Visit 10) in the following measures compared to placebo: 
 
• Total lung capacity (TLC)
 
• RV/TLC ratio
 
• Inspiratory capacity (IC)
 
• Functional residual capacity (FRC)
 
• Vital capacity (VC)
 

Sub-study Exploratory Objective	Outcome Measures
To determine the effect of benralizumab on the time course of change in lung function as assessed through body plethysmography	Change from baseline (Visit 4) to end of treatment (Visit 10) in the following measures compared to placebo: 
 
• Specific airway conductance (SGaw)
 
• Airway resistance (Raw)
 

## 1.2 Study design

This is a randomized, double-blind, parallel group, placebo-controlled study designed to evaluate the onset of effect and safety of a fixed 30 mg dose of benralizumab administered subcutaneously (SC) to patients with severe, uncontrolled asthma. Approximately 230 patients with peripheral blood eosinophil counts  $\geq 300$  cells/ $\mu$ L will be randomized globally to receive SC benralizumab 30 mg or placebo.

After enrolment, eligible patients will enter a 5-week screening/run-in period. Patients who meet eligibility criteria will enter a 12-week treatment period and receive 30 mg benralizumab or placebo at Day 0, Day 28 (+/- 3 days), and Day 56 (+/- 3 days). An End-of-Treatment (EOT) visit will be conducted at Day 84 (Week 12) and a follow-up (FU) visit will be conducted at Day 112 (Week 16).

See the clinical study protocol (CSP) Section 4, Tables 2 and 3 for a detailed list of visits and assessments.

## 1.3 Number of subjects

The study will recruit approximately 230 patients in total and 115 patients in each treatment group based on the primary objective of the study to determine the effect of benralizumab on the time course of change (onset and maintenance of effect) of pre-bronchodilator (BD) FEV1.

Patients will be randomized in a 1:1 ratio to benralizumab or placebo. In order to have a balanced number of patients for each region and the body plethysmography sub-study, the randomization will be stratified by these variables.

The study is powered for the primary objective of the study to determine the effect of benralizumab on the time course of change (onset and maintenance of effect) of pre-BD FEV1.

The first post-baseline timepoint where the p-value for the mean difference between benralizumab and placebo is  $\leq 0.05$  will be used to determine time to onset of effect. The average over the mean differences between benralizumab and placebo based on the change from baseline (Visit 4) to Days 28 (Visit 8), 56 (Visit 9), and 84 (Visit 10) in pre-BD FEV1 will be used to determine if the study is positive and to determine maintenance of effect.

The results of the Phase 2b study, MI-CP220 (Castro et al 2014) and the Phase 3 asthma exacerbation studies, SIROCCO (Bleeker et al 2016) and CALIMA (Fitzgerald et al 2016) were used as a basis for the sample sizing. From these studies, it is expected that around 115 patients per treatment arm (230 in total) will provide approximately 90% power for the primary endpoint pre-BD FEV1 with type I error controlled at a two-sided alpha level of 0.05 if the true average over the mean treatment differences (benralizumab – placebo) across Days 28 (Visit 8), 56 (Visit 9), and 84 (Visit 10) is 138 mL. The sample size will also be sufficient to have approximately 80% power for an average over the mean treatment difference of 120 mL. The assumed variability has a within-group standard deviation of 375 mL and within-patient correlation of 0.6. If the within-patient variability is reduced to 350 mL, the sample size would be sufficient 80% power for an average of 110 mL. In addition, it is expected that around 115 patients per treatment arm will have 80% power to detect a true treatment difference (benralizumab – placebo) of 130 mL, assuming a within-group standard deviation of 350 mL or a true treatment difference of 140 mL, assuming a standard deviation of 375 mL. Based on these assumptions, the minimum difference that would be statistically significant at the 5% level ranges from approximately 85 to 100 mL. The sample size was estimated using nQuery + nTerim version 3.0 using methodology by Liu et al (Liu et al 2005).

## **2. ANALYSIS SETS**

### **2.1 Definition of analysis sets**

Five analysis sets are defined below:

- All patient analysis set
- Full analysis set (FAS)
- Sub-study analysis set
- Safety analysis set
- Pharmacokinetics (PK) analysis set

Patients must have provided their informed consent. If no signed informed consent is collected (major protocol deviation), the patient will be excluded from all analysis sets defined below.

All efficacy will be performed according to the Intent-to-Treat (ITT) principle based on the FAS. For consistency, demographic and baseline characteristics will be presented using the FAS. Safety objectives will be analyzed based on the safety analysis set.

### **2.1.1 All patients analysis set**

This analysis set comprises all patients screened for the study and will be used for reporting of disposition and screening failures.

### **2.1.2 Full analysis set**

All patients randomized and receiving at least 1 dose of investigational product (IP) will be included in the FAS, irrespective of their protocol adherence and continued participation in the study. Patients will be analyzed according to their randomized treatment, irrespective of whether or not they have prematurely discontinued, according to the ITT principle. Patients who withdraw consent, and assent when applicable, to participate in the study will be included up to the date of their study termination. All efficacy and patient-reported outcome (PRO) data will be based on this analysis set.

### **2.1.3 Body plethysmography sub-study analysis set**

The subset of patients who are randomized as part of the body plethysmography sub-study and receive any IP will be analyzed as described for the FAS.

### **2.1.4 Safety analysis set**

All patients who received at least 1 dose of IP will be included in the safety analysis set. Patients will be classified according to the treatment they actually received. A patient who has on 1 or several occasions received active treatment will be classified as active. All safety summaries and anti-drug antibodies (ADA) analyses will be based on this analysis set.

### **2.1.5 Pharmacokinetic analysis set**

All patients who received benralizumab and from whom PK blood samples are assumed not to be affected by factors such as protocol violations and who had at least 1 evaluable serum PK observation post first dose will be included in the PK analysis set. All PK summaries will be based on this analysis set.

## **2.2 Violations and deviations**

Patients who do not meet eligibility criteria but are still randomized will be analyzed according to the analysis sets described in Section 2.1. There is no intention to perform a per-protocol analysis in this study.

### **2.2.1 Important protocol deviations**

Important deviations will be those which are considered to potentially impact upon the interpretation of the primary endpoint in the study. Only important protocol deviations will be listed and tabulated in the CSR.

The following categories of protocol deviations will be reviewed by medical advisors and statisticians prior to database lock to determine those which are considered important deviations as outlined below, with additional details provided in [Appendix 8.3](#):

- Patients who do not meet key inclusion criteria (patients incorrectly randomised)
- Patients who meet any of the key exclusion criteria (patients incorrectly randomised)
- Patients who developed IP discontinuation criteria during the study but were not discontinued
- Patients who received prohibited/restricted concomitant medication(s)
- Deviations from study procedures

Patients for whom significant protocol deviations were recorded that impact the interpretation of the study safety outcomes will have a footnote added to applicable output to describe the deviation and its potential impact. Such patients will be identified as part of the protocol deviation review process prior to database lock.

Patients who received incorrect study treatment will be identified after database lock and unblinding. Patients will be classified according to the treatment they actually received for the safety analysis set according to the following rules, based on the unblinded data from the Interactive Voice Response System (IVRS) system:

- Patients assigned to benralizumab treatment regimen who receive only placebo will be assigned to the placebo group.
- Patients assigned to the placebo group who received 1 or more doses of benralizumab will be assigned to the benralizumab group.

### **2.2.2 Visit window definitions**

No visit windows will be defined for screening visits. For local laboratory and all vital signs, safety labs other than white blood cell (WBC) cell count and differentials, and ADA/neutralizing antibodies (nAb), the visit recorded in web-based data capture (WBDC) will be used. For endpoints that present visit-based data including WBC cell count and differentials (including eosinophil count data), spirometry, FeNO, body plethysmography (sub-study), and patient reported outcomes (PROs), the variables will be summarized based on the scheduled days with adjusted analysis-defined visit windows. The adjusted analysis-defined visit windows will be based on the collection schedule listed in the protocol and variables will be windowed to the closest scheduled visit for that variable.

The adjusted analysis-defined visit windows for assessments conducted are summarized in [Table 1](#).

**Table 1 Visit windows for assessments**

Adjusted defined windows visit	Scheduled study day	Maximum windows
Week 0 (Day 0)	1	Study Day=1
Day 3	4	$2 \leq \text{Study Days} \leq 5$
Day 7	8	$6 \leq \text{Study Days} \leq 11$
Day 14 (Week 2)	15	$12 \leq \text{Study Days} \leq 22$
Day 28 (Week 4)	29	$23 \leq \text{Study Days} \leq 42$
Day 56 (Week 8)	57	$43 \leq \text{Study Days} \leq 70$
Day 84 (Week 12/EOT)	85	$71 \leq \text{Study Days} \leq 98$
Day 112 (Week 16/Follow-up)	113	$99 \leq \text{Study Days}$

For assignment of data to adjusted analysis-defined visit windows, study day will be defined as follows: (Date of assessment – date of randomization) +1

For example, by this definition, the day of randomization will be Study Day 1 and the planned date of Week 4 will be Study Day 29 (=28+1).

If multiple assessments are recorded within a single visit window, please refer to the rules below:

- If there are 2 or more observations within the same visit window, then the non-missing one closest to the scheduled visit will be used in the analysis.
- If 2 observations are equidistant from the scheduled visit, then the non-missing observation with the earlier collection date will be used in the analysis.
- If 2 observations are collected on the same day, then the non-missing one with the earlier collection time will be included in the analysis.

If a visit window does not contain any observations, then the data will remain missing.

For pre-BD FEV1 (L) and body plethysmography data, the non-missing value with acceptable quality (acceptable or borderline quality grade) which is closest to the scheduled visit will be included in the analysis. For post-BD FEV1, the highest value with acceptable quality from the same date as the pre-BD FEV1 result will be used.

### 2.2.3 The definition of baseline

In general, the last recorded value on or prior to the date of randomization will serve as the baseline measurement for efficacy endpoints, while the last recorded value prior to first dose of study treatment will serve as the baseline measurement for safety endpoints. If there is no value prior to randomization (or the first dose of study treatment, depending on the endpoint), then the baseline value will not be imputed and will be set to missing. No data known to be

collected post first dose will be used in determining the baseline value, unless otherwise specified.

For categorical (yes/no) baseline respiratory disease characteristics, if 'yes' is indicated in any visit during enrollment (scheduled or unscheduled), 'yes' will be used.

There are 2 pre-BD spirometry assessments – 30 and 60-mins prior to IP administration on Day 0 of randomization visit. Day 0 pre-BD FEV1 value will be set to:

- The average of the two if both have acceptable quality, or
- the value of the one with acceptable quality if only 1 has acceptable quality, or
- missing, if none of the two has acceptable quality

Day 0 pre-BD value of FVC, FEF 25-75% and ratio of FEV1/FVC will be calculated using the same logic as for Day 0 pre-BD FEV1.

For pre-BD FEV1 (L) and sub-study assessments from whole body plethysmography, the last non-missing value with acceptable quality (acceptable or borderline quality grade) on or prior to the date of randomization will be used as baseline. The first dose of study treatment is scheduled to be administered on the date of randomization (Visit 4); however, if the first dose of study treatment is delayed until after the date of randomization, the last recorded value with acceptable quality prior to the first dose of study treatment will be used as baseline measurement for spirometry parameters. Baseline of pre-BD FVC will be assigned in the same way as for pre-BD FEV1.

For FeNO, the mean of repeated assessments at Week 0 (Visit 4) prior to randomization will be used as baseline values. If the first dose of study treatment is delayed until after the date of randomization, the mean of last recorded values prior to the first dose of study treatment will be used as baseline. If the assessments prior to randomization/first dose are missing, the mean value from Day -21 (Visit 2) will be used for baseline.

ACQ-6, SGRQ, and PGI-S assessments at Week 0 (Visit 4) prior to randomization will be used for calculating the respective baselines. For ACQ-6, if the value at Week 0 (Visit 4) is missing, the non-missing value from Day -35 (Visit 1) will be used for baseline.

For summaries of vital signs and laboratory results by visit and in the calculation of change from baseline, the last non-missing assessment prior to first dose of study treatment will be used as baseline.

#### **2.2.4 Prior/concomitant medications**

All patients are required to be treated with stable dose inhaled corticosteroids (ICS)/ Long-acting  $\beta_2$  agonists (LABA) for at least 30 days prior to Visit 1 and during the course of the study.

The background asthma controller medications should be maintained at a stable dose from Visit 1 until the end of the study. No changes are allowed to background medications throughout the duration of the study except during the treatment of an asthma exacerbation.

Short-acting  $\beta_2$  agonists (SABAs) may be used as rescue medication during the study in the event of a worsening of asthma symptoms.

A medication will be regarded as 'prior' if it was stopped on or before the date of randomization (medication stop date  $\leq$  date of randomization).

A medication will be regarded as 'concomitant' if the start date is after the date of randomization, or if it started on or prior to the date of randomization and was ongoing after the date of randomization.

### **3. EFFICACY AND SAFETY VARIABLES**

#### **3.1 Primary efficacy outcome variable**

The primary efficacy variable is the change from baseline in pre-BD FEV1. Details regarding the definition of baseline for pre-BD FEV1 are provided in Section 2.2.3.

#### **3.2 Secondary efficacy outcome variables**

##### **3.2.1 FEV1 responder**

A FEV1 responder at each post-baseline visit will be defined as a patient who had improvement on FEV1 by the following cut-offs: 50, 100, 150, 200, 250 and 300 mL, ie, a subject with a change from baseline in FEV1 greater than or equal to the cut-off at a visit will be categorized as a responder at that visit. A patient with missing value of change from baseline at a visit will be excluded from the calculation of proportion of responders at that visit.

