#### **4.2.6.2 Proportion of responders by PRO measures**

Responder at the post-baseline visit from the selected secondary endpoints below will be analyzed using a logistic regression model with repeated measures using generalized equation estimate method. The model will include treatment, region, visit and treatment group by visit interaction as fixed factors, and baseline scores as a covariate. The variance-covariance matrix will be assumed to be unstructured.

ACQ-6 responder at each post-baseline visit: Will be based on change from baseline to each post-baseline visit as defined in Section 3.3.2. Patients with missing or non-evaluable score at a post-baseline visit will be considered non-responders.

SGRQ responder at each post-baseline will be defined for each post-baseline visit as an individual with a  $\geq 4$ -point decrease (improvement) from baseline in SGRQ total score. Patients with missing or non-evaluable score at any post-baseline visit will be considered non-responders.

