#### *Missing data descriptions*

Tabular summaries for the percentage of patients by the reason for discontinuation of randomized treatment as well as for withdrawal from the study will be presented by treatment to describe why patients discontinue from randomized treatment or withdraw from the study. The time to discontinuation of randomized treatment and withdrawal from the study will be presented using Kaplan Meier plots (overall and split by treatment related/not treatment

related reason for discontinuation, as defined in Tables 1 and 2). Dependent on these outputs additional exploratory analyses may be produced as deemed necessary to further understand the pattern of missing data.

Primary analysis under the Treatment Policy Estimand using the Missing at Random assumption

The primary analysis of the pre-BD FEV1 is under the treatment policy estimand which allows for differences in outcomes over the entire study treatment period to reflect the effect of initially assigned randomized treatment as well as if subsequent treatments are taken. This primary analysis includes all data until patients withdraw from the study regardless of if they discontinue from randomised treatment. The Mixed Model Repeated Measures model (MMRM) used is a direct likelihood approach (DL) which is valid under the Missing at Random (MAR) assumption.

Sensitivity analysis under the Treatment Policy Estimand using both MAR and MNAR assumptions

To examine the sensitivity of the results of the primary analysis to departures from the underlying assumptions, sensitivity analyses of the repeated measures analyses will be performed for the pre-BD FEV1 using controlled sequential multiple imputation methods based on pattern mixture models, as described in the European Medicines Agency Guideline on Missing Data in Confirmatory Clinical Trials ([EMA 2010](#)). As with the primary analysis, the sensitivity analyses include all data until patients withdrew from the study regardless of if patients discontinue from randomised treatment.

The imputation process consists of a sequence of multiple imputation (MI) steps, where each step is intended to impute missing values at 1 timepoint only. This model will assume that some pre-specified subset of patients who withdraw from the study have correlations with future (unobserved) visits similar to patients in the placebo arm. This allows us to assess various deviations from the MAR assumption.

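### Responder analyses exclude missing FEV1 visits but count missing ACQ-6 and SGRQ visits as failures; the FEV1 rule needs more than MAR, and one SGRQ word is ambiguous

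*SAP*

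**What the plan says.** **FEV1 responders.** SAP 3.2.1 defines response at each visit at six cut-offs from 50 to 300 mL and adds that a patient without a change value at a visit "will be excluded from the calculation of proportion of responders at that visit". SAP 4.2.6.1 fits a repeated-measures logistic GEE with treatment, region, visit, treatment by visit and baseline FEV1. It does not say how that model treats a missing visit; leaving it out is the natural reading of 3.2.1.

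**ACQ-6 responders.** SAP 4.2.6.2 uses the same form of GEE, with the rule: "Patients with missing or non-evaluable score at a post-baseline visit will be considered non-responders".

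**SGRQ responders.** Same section and model, but the rule reads: "Patients with missing or non-evaluable score at any post-baseline visit will be considered non-responders". The sentence before it says that response "will be defined for each post-baseline visit as an individual with a" reduction of at least 4 points.

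**Primary FEV1 analysis.** SAP Appendix 8.1 describes the MMRM as a direct-likelihood method "which is valid under the Missing at Random (MAR) assumption". Multiple imputation under MAR and under the dropout-reason approach (DRMI) is planned as sensitivity analysis for the repeated-measures analysis of pre-BD FEV1. None is planned for a responder endpoint. No reason is given for the differing responder rules.

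**The concern.** Three responder endpoints share a model and will be reported in the same study, but a missed visit does not mean the same thing in each. A gap between the FEV1 and questionnaire results could therefore come partly from the rule and not from the drug.

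The FEV1 rule raises a further point. The MMRM allows dropout to depend on FEV1 already observed after baseline. An unweighted GEE on available visits does not: in general it needs missingness to be completely random or explained by its own covariates. Once FEV1 is dichotomised, the same measurements carry a stronger assumption than in the primary analysis, and no planned sensitivity analysis of this model tests it.

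The SGRQ wording is a separate matter. Read literally, one missed questionnaire would make a patient a non-responder at every visit, including visits with a measured response. Two programmers could produce different results from the same sentence.

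**Working it through.** **Inputs.** The rules come from SAP 3.2.1 and 4.2.6.2. The three SGRQ visits in the treatment period are Days 28, 56 and 84 (protocol Table 3). The documents state no response rate, missing rate or power for any responder endpoint, so there is no plan figure to reproduce on this point. All rates below are assumptions. Notation: p = true response, m = proportion missing at a visit.

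**1. Exclusion when every missing patient is a failure.** The observed proportion is p/(1−m). True response 60% v 45%: difference 15.0 points, OR (0.60/0.40)/(0.45/0.55) = 1.83.

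| Missing, benralizumab v placebo | Observed | Difference | OR |
|---|---|---|---|
| 5% v 5% | 63.2% v 47.4% | 15.8 | 1.90 |
| 10% v 10% | 0.60/0.90 = 66.7% v 0.45/0.90 = 50.0% | 16.7 | 2.00 |
| 3% v 10% | 61.9% v 50.0% | 11.9 | 1.62 |
| 10% v 3% | 66.7% v 46.4% | 20.3 | 2.31 |

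Exclusion inflates each arm's percentage. The treatment difference can move either way, depending on which arm has more gaps. In this mechanism the failure rule is correct. If missingness is unrelated to response, exclusion is unbiased at 15.0 points.

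**2. Failure rule when missingness is unrelated to response.** The observed proportion is p(1−m).

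- True 60% v 45%, 3% missing in each arm: 58.2% v 43.65%, difference 14.55 points instead of 15.0.
- The same with 10% in each arm: 54.0% v 40.5%, difference 13.5 points.
- No true effect, 50% in both arms, 3% v 10% missing: 0.50 × 0.97 − 0.50 × 0.90 = 3.5 points of false difference.

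So this rule can also be biased, most visibly when gaps differ by arm.

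**3. The two readings of the SGRQ sentence.** True 50% v 35%, 5% missing per visit in each arm, unrelated to response.

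- Visit-specific: (0.50 − 0.35) × 0.95 = 14.25 points.
- Literal, gaps independent across three visits: 0.15 × 0.95³ = 0.15 × 0.857 = 12.9 points.
- Literal, the same patients missing all three visits: 0.15 × 0.95 = 14.25 points, identical to the visit-specific reading.

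With unequal gaps the readings differ more. For 8% on benralizumab v 4% on placebo, visit-specific gives 0.50 × 0.92 − 0.35 × 0.96 = 12.4 points. Literal with independent gaps gives 0.50 × 0.92³ − 0.35 × 0.96³ = 38.9 − 31.0 = 8.0 points (from unrounded values). Full overlap again gives 12.4.

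**The case against.** The strongest reply is that little turns on this. SAP 4.1 makes every p-value outside the primary analysis nominal, protocol 8.5.2.1 calls the ACQ-6 and SGRQ responder analyses supportive, and no section plans a formal comparison across the three endpoints. Patients are asked to stay in follow-up after stopping treatment, which should limit gaps. That stands, and it limits the importance of the point.

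A reader might infer that there are three distinct rules. The documents do not establish that. SGRQ response is defined visit by visit in both SAP 3.2.5 and 4.2.6.2, and the model has visit and treatment-by-visit terms. In that setting *any* most naturally means whichever visit is missing, which is the ACQ-6 rule. Two rules and one loose word are certain.

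A reader might also infer that the FEV1 GEE strictly requires data missing completely at random. That is too strong, since missingness explained by treatment, region, visit and baseline FEV1 is tolerated.

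Nor is exclusion the SAP's only treatment of missing FEV1 response. The Bayesian model in 4.2.5.4 estimates proportions at the same six cut-offs and extrapolates patients who withdraw. That is a useful complement, but it is a separate supportive analysis based on fitted curves and does not repair the GEE.

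**Conclusion.** The point holds as a minor one. FEV1 responders are analysed on available visits and ACQ-6 and SGRQ responders with gaps counted as failures, under the same GEE and without a stated reason. The FEV1 version rests on a stronger missing-data assumption than the primary MMRM on the same data. The SGRQ wording is ambiguous, with the context favouring the visit-specific reading.

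It would be tempting to call one rule sound and the others biased. The calculations do not support that: each can be biased under some missingness mechanism, and the direction depends on who is missing.

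The size cannot be fixed from the documents. Under the assumed rates, 10% missing per arm with all missing patients failing moves the FEV1 OR from 1.83 to 2.00. This is an extreme case, chosen to show how far exclusion can move. MAR methods would not be protected in it either, unless earlier values explained the gaps. At 5% missing in each arm, the SGRQ reading matters by at most 14.25 − 12.9, about 1.4 points, with independent gaps as the comparison, and by nothing if gaps fully overlap. At 3% in each arm, the failure rule costs under half a point. The primary MMRM conclusion is not affected.

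**What to change.** 1. **SGRQ wording.** In SAP 4.2.6.2, replace *at any post-baseline visit* by *at that visit*.
2. **FEV1 responders.** Derive responder status at each cut-off from the imputed FEV1 datasets already planned in Appendix 8.1 (MAR, with DRMI as sensitivity). Fit the GEE in each and combine with PROC MIANALYZE. State a fallback working correlation in case the unstructured form does not converge; 4.2.6.1 gives none.
3. **Common reading.** Report FEV1 responders with missing counted as non-response as a sensitivity analysis, so that they can be read on the same rule as ACQ-6 and SGRQ.
4. **Cross-references.** 4.2.6.2 points to 3.3.2 for the ACQ-6 definition, which is in 3.2.4. 4.2.6.1 points to 3.1 for the FEV1 cut-offs, which are in 3.2.1.

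**Cost.** A few SAP sentences and more model fits: with 100 imputations under each assumption, 6 × 100 × 2 = 1,200 GEE fits. FEV1 responder percentages may be slightly lower than under exclusion. The design, sample size and primary analysis do not change.
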